### 1. Participant Flow

#### Recruitment Details

This will be an observational prospective cohort study conducted at Obstetrics and Gynecology Department of Cengiz Gokcek Obstetrics and Children's Hospital between January 2020 and June 2021. The authors will be recruited 50 subjects with idiopathic POI, and 50 healthy patients were selected for the control group. All patients will be given their oral and written informed consent before their inclusion in the study. The protocol was approved by the Ethics Committee for Clinical Research of Gaziantep University (Reference number: 2020/362). The study strictly will be adhered to the principles of the Declaration of Helsinki.

#### Pre-assignment Details

The authors first will be assessed the recruited people to ensure meeting the inclusion and exclusion criteria. The inclusion criteria will be made according to the official documents.

#### Arm/Group Information \*

There are two groups in the study.

## **Arm/Group Title \***

Premature ovarian insufficiency group

Control group

## **2. Baseline Characteristics**

In order for the expectation that a medium effect size ( $d = 0.60$ ) would occur between the physiological parameters of the POI group and the control group was statistically significant, the required minimum number in each group was determined as 45 ( $\alpha=0,05$ ;  $1-\beta=0,80$ ). It was decided to include the same number of participants of control groups to balance the POI and control groups. Power analysis was performed by using G power package version 3.9.1. Kolmogorov Smirnov and Shapiro Wilk tests will be used to test the normal distribution of data. For comparing groups (POI/control) the student t-test will be used for variables that have a normal distribution, and the Mann Whitney U test will be used for variables that have not a normal distribution. The ROC analysis will be applied for the determination of cut-off point for variables. Moreover, Spearman correlation test will be used for the relationship of between variables. SPSS for Windows 22.0 and Medcalc programs will be used for statistical analysis.  $p<0.05$  will be accepted as statistical significance.

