## **4. Endpoints of the study:**

The primary outcome in these analyses will compare Lead (Pb), Cadmium (Cd), Gadolinium (Gd), Arsenic (As), Mercury (Hg), Cobalt (Co), Vanadium (V), Titanium (Ti), Sulfur (S), Chromium (Cr), Silver (Ag), Molybdenum (Mo), Boron (B), Lithium (Li), and Nickel (Ni) levels in the idiopathic POI group and control group.

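### Does naming two normality tests, without saying which one decides, undermine the primary comparisons of the 15 elements?

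*Combined protocol and SAP*

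**What the plan says.** Section 2 (Baseline Characteristics) sets the rule in three steps. First, "Kolmogorov Smirnov and Shapiro Wilk tests will be used to test the normal distribution of data". Variables judged normal are then compared with a Student t-test. For the others, the plan states that "the Mann Whitney U test will be used for variables that have not a normal distribution". No transformation is mentioned, so the t-test would be on the raw scale. The section gives no level for the normality tests. It does not say whether they are run by group or pooled, whether Kolmogorov-Smirnov (KS) is corrected for estimated parameters, or which test prevails if they differ.

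Sections 3 and 4 make 15 element concentrations primary, each compared between the premature ovarian insufficiency group and the controls. The sample size in section 2 expects that "a medium effect size ( $d = 0.60$ ) would occur between the physiological parameters", from which "the required minimum number in each group was determined as 45". Recruitment Details plans 50 per group.

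**The concern.** The test for each primary outcome is fixed only after its distribution has been seen, and the two gatekeepers differ in sensitivity. Concentration data are often skewed, and Shapiro-Wilk detects skew more readily than KS. Two analysts could therefore follow the text faithfully, run different tests on the same element and report different verdicts.

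Three harms would be at stake:

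- **Error rate.** An analyst could choose the more favourable test, with 15 opportunities to do so.
- **Power.** If the less sensitive KS result is followed, skewed data could go to a raw-scale t-test.
- **Interpretation.** Some elements would be reported as differences in means and others as rank comparisons.

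**Working it through.** **Inputs from the documents.** d = 0.60, alpha 0.05, power 0.80, minimum 45 per group (section 2); 50 per group planned (Recruitment Details); 15 primary outcomes (sections 3 and 4). Sidedness is not stated; two-sided is assumed because it reproduces 45, whereas one-sided gives 35-36.

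**Step 1: the plan's own figure.** Normal approximation: n = 2(1.960 + 0.842)²/0.60² = 43.6, so 44. With the noncentral t, n = 44.59, so 45, as stated. Power is 0.804 at 45 and 0.844 at 50 per group. For Mann-Whitney on normal data, n = 44.59 × π/3 = 46.7, so 47, which the planned 50 covers.

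**Step 2: simulate the rule.** Assumptions: log-normal data, log-scale SD σ from 0 (normal) to 1.0, 50 per group, and a shift of zero or 0.6 SD on the log scale. A variable is non-normal if either group rejects at 0.05. There are 10,000 replicates per cell, with KS corrected for estimated parameters. SW is Shapiro-Wilk. Paired entries in the conflict and verdict columns are null / shifted; in the type I and power columns they are SW followed / KS followed.

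| σ | SW and KS conflict (%) | Type I, SW / KS | Power, SW / KS | Verdict depends on choice (%) |
|---|---|---|---|---|
| 0 | 11.6 / 11.5 | 0.053 / 0.053 | 0.848 / 0.848 | 0.3 / 0.7 |
| 0.15 | 24.9 / 23.7 | 0.053 / 0.050 | 0.838 / 0.836 | 0.7 / 1.3 |
| 0.25 | 32.5 / 31.1 | 0.053 / 0.053 | 0.824 / 0.826 | 0.7 / 1.9 |
| 0.35 | 25.2 / 25.4 | 0.054 / 0.056 | 0.828 / 0.832 | 0.8 / 1.3 |
| 0.5 | 8.0 / 8.0 | 0.051 / 0.052 | 0.822 / 0.823 | 0.1 / 0.5 |
| 0.75 | 0.3 / 0.2 | 0.049 / 0.049 | 0.828 / 0.828 | 0.01 / 0.02 |
| 1.0 | 0.0 / 0.0 | 0.047 / 0.047 | 0.825 / 0.825 | 0.0 / 0.0 |

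The Monte Carlo standard error of a 5% rate is √(0.05 × 0.95/10,000) = 0.0022. In the σ = 0.35 cell with the highest type I error (0.056), the log-scale t-test, which is exact there, also came out at 0.054, so part of that excess is chance.

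**Step 3: compare with one fixed test** (power at the 0.6 SD shift).

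| σ | Raw t always | Mann-Whitney always | Log-scale t always | Plan's rule, uncorrected KS |
|---|---|---|---|---|
| 0 | 0.848 | 0.831 | 0.848 | 0.848 |
| 0.25 | 0.827 | 0.816 | 0.842 | 0.828 |
| 0.5 | 0.799 | 0.822 | 0.842 | 0.814 |
| 0.75 | 0.747 | 0.828 | 0.848 | 0.827 |
| 1.0 | 0.657 | 0.825 | 0.843 | 0.825 |

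A raw t-test used regardless loses 0.848 − 0.747 = 10 points at σ = 0.75 and 0.843 − 0.657 = 19 points at σ = 1.0, against the log-scale t-test. The plan does not use it there: with corrected KS the two normality tests both reject in nearly every replicate, and the variable goes to Mann-Whitney. The plan's largest loss against the log-scale t-test is 0.842 − 0.822 = 2.0 points at σ = 0.5, or 0.842 − 0.814 = 2.8 points with uncorrected KS.

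**Step 4: opportunism.** Always keeping the smaller of the two p-values gives a per-test error of 6.5-7.5%, but that ignores the written rule. The gap leaves a choice only where the normality tests conflict. Limiting the choice to those cases gave null rejection rates from 4.95% to about 5.7% across separate simulation runs with corrected KS. With uncorrected KS, where conflict is far more frequent, it reached 6.6-7.2% at σ of 0.35-0.5.

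**The case for a change.** The strongest case is about pre-specification. With mild to moderate skew, roughly a quarter of the primaries, about four of 15, would have no uniquely defined test. If each outcome independently carried the largest simulated risk, the chance that at least one of 15 verdicts depends on the analyst is 1 − 0.981^15 = 25%; with no true differences it is 1 − 0.9924^15 = 11%. At a smaller shift of 0.4 SD the per-outcome figure rises to 2.1-2.7%. Naming one method costs only a sentence.

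The arithmetic stands, but it takes the worst σ for every element. Such reversals occur where two valid p-values fall on either side of 0.05. They leave the long-run error rate and power of the analysis almost unchanged, whichever normality test is followed. They would be a real weakness only with an analyst who chooses for the result and also uses uncorrected KS.

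The complaint about mixed estimands carries less weight. Sections 3 and 4 plan a group comparison within each element; they plan no ranking or pooling across elements. The ROC and Spearman analyses in section 2 do not pass through the normality gate.

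**Conclusion.** The concern does not call for a change. Section 2 leaves a detail open, but an analyst who follows it with either normality test, at the conventional 5% level and by group, gets a sound test. Type I error is 4.7-5.6%, power is 82-85% at 50 per group, and the verdict depends on the choice in at most 1.9% of outcomes at zero or 0.6 SD shift. Mann-Whitney throughout would cost 1.7 points on normal data (0.848 − 0.831) and gain at most 0.8 points (0.822 − 0.814, with uncorrected KS at σ = 0.5). A log-scale t-test would gain about 2 points, 3 at most, under a log-normal shape that the documents do not establish. Preferring either is a matter of judgement.

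This rests on log-normal data with log-scale SD up to 1.0, two-sided tests, and an analyst who keeps to the written rule. Ties and values below a detection limit were not modelled. A sentence saying which normality test governs would be harmless tidying, but the primary comparisons do not depend on it.

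### The 15-element POI-versus-control comparison is observational but planned only as unadjusted tests; an age-adjusted main analysis is a cheap improvement

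*Combined protocol and SAP*

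**What the plan says.** Recruitment Details describes the design: "This will be an observational prospective cohort study". It gives 50 women with idiopathic POI and says of the comparison group that "50 healthy patients were selected for the control group". How the controls were chosen is not described further.

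On eligibility, Pre-assignment Details says only that "The inclusion criteria will be made according to the official documents". Those documents are not part of the text available here, so an age restriction or matching may be specified there.

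Section 4 (Endpoints of the study) makes the primary outcome a comparison of 15 named elements: "levels in the idiopathic POI group and control group".

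Section 2 (Baseline Characteristics) sets out the analysis. For the group comparison it says "For comparing groups (POI/control) the student t-test will be used for variables that have a normal distribution". Elements that fail the normality check get a rank test instead, again without covariates: "the Mann Whitney U test will be used for variables that have not a normal distribution". It adds "The ROC analysis will be applied for the determination of cut-off point for variables" and a Spearman correlation, neither of which adjusts the group comparison. No regression, stratification or matching is mentioned. The one reference to balance concerns numbers: "It was decided to include the same number of participants of control groups to balance the POI and control groups".

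**The concern.** Because group membership is not randomised, the two groups may differ in characteristics other than POI. Equal group sizes do not prevent that. A covariate distorts the comparison of an element only if both conditions hold: it differs between the groups, and it is associated with that element. Age is the natural example to write into a plan, but nothing in the documents shows that age, or anything else, differs here.

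If such a covariate exists, the t-test or Mann-Whitney test picks up the covariate's contribution along with any contribution of POI. It may then report a difference that is not due to POI, or miss one that is. Recruiting more women only estimates the distorted difference more precisely. The planned ROC analysis uses the same unadjusted concentrations, so its results carry the same shift.

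**Working it through.** **Inputs from the documents.** 50 per group (Recruitment Details); d = 0.60, alpha 0.05, power 0.80 and a minimum of 45 per group (section 2). Sidedness is not stated.

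**The plan's own figure.** For a two-sided two-sample t-test the noncentrality is d × √(n/2). With n = 45 this is 0.60 × √22.5 = 2.85, and power is 0.804. The minimum of 45 is therefore reproduced exactly by a two-sided test; a one-sided test would need 36. At the planned 50 per group the noncentrality is 0.60 × √25 = 3.0 and power is 0.844 (0.825 for Mann-Whitney, by simulation). The sample size is not in dispute.

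**Assumed inputs.** The documents give neither of these:
- r, the within-group correlation between the covariate and the element: 0.1 to 0.4.
- g, the difference in covariate means between groups, in within-group SDs: 0.25, 0.5 or 1.

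**Formulas (50 per group, two-sided 0.05).**
- Shift in the unadjusted standardised difference: r × g.
- False-positive rate with no true adjusted difference: noncentral t, df 98, noncentrality 5 × r × g.
- Masked power, with a true d of 0.60 and the covariate acting in the opposite direction: noncentrality 5 × (0.60 − r × g).
- Age-adjusted power: df 97, noncentrality 5 × 0.60 / √[(1 + g²/4)(1 − r²)].
- Expected ROC area with no true difference: Φ(r × g / √2).

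Example at r = 0.3, g = 0.5: the shift is 0.15, so the noncentrality is 0.75 and the false-positive rate is 0.115. Masked power uses 5 × 0.45 = 2.25, giving 0.606. Adjusted power uses 3.0 / √(1.0625 × 0.91) = 3.05, giving 0.856. The ROC area is Φ(0.106) = 0.542.

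| r | g (SD) | Shift | False positive, t | False positive, Mann-Whitney (simulated) | Masked power, t | Age-adjusted power, linear | Null ROC area |
|---|---|---|---|---|---|---|---|
| 0.1 | 0.25 | 0.025 | 0.052 | 0.051 | 0.812 | 0.842 | 0.507 |
| 0.1 | 0.5 | 0.05 | 0.057 | 0.057 | 0.777 | 0.825 | 0.514 |
| 0.1 | 1 | 0.10 | 0.079 | 0.077 | 0.697 | 0.761 | 0.528 |
| 0.2 | 0.25 | 0.05 | 0.057 | 0.056 | 0.777 | 0.853 | 0.514 |
| 0.2 | 0.5 | 0.10 | 0.079 | 0.078 | 0.697 | 0.837 | 0.528 |
| 0.2 | 1 | 0.20 | 0.168 | 0.161 | 0.508 | 0.774 | 0.556 |
| 0.3 | 0.25 | 0.075 | 0.066 | 0.064 | 0.739 | 0.871 | 0.521 |
| 0.3 | 0.5 | 0.15 | 0.115 | 0.108 | 0.606 | 0.856 | 0.542 |
| 0.3 | 1 | 0.30 | 0.318 | 0.303 | 0.318 | 0.795 | 0.584 |
| 0.4 | 0.25 | 0.10 | 0.079 | 0.078 | 0.697 | 0.895 | 0.528 |
| 0.4 | 0.5 | 0.20 | 0.168 | 0.161 | 0.508 | 0.882 | 0.556 |
| 0.4 | 1 | 0.40 | 0.508 | 0.487 | 0.168 | 0.826 | 0.611 |

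For reference, a true d of 0.60 with no imbalance gives a ROC area of Φ(0.60/√2) = 0.664.

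**Reading the table.** The t-test false-positive rate stays below 8% in 7 of the 12 rows and reaches 10% only when r × g is at least 0.132. In simulation (40,000 runs per row) the age-adjusted false-positive rate is 0.048 to 0.051 for the linear model and 0.048 to 0.053 for the rank model. Simulated linear power is 0.756 to 0.892, in line with the formula. Simulated rank-model power is 0.745 to 0.877. When the covariate acts against the group effect at g = 1, rank-model power is a little lower, at about 0.74 (r = 0.1) and 0.80 (r = 0.4). With no age gap, adjusting costs essentially nothing: linear power is 0.844 at r = 0 and 0.876 at r = 0.3.

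**The case against.** The strongest objection is that the harm is conditional on facts nobody can see in this text. Age is not mentioned, control selection is a single clause, and eligibility sits in documents that are not available. If the controls were matched on age or drawn from a narrow age range, bias from age is small and the main example largely falls away. Both r and g are assumed, and the worst case depends on where the grid stops: taking r up to 0.5 would raise the upper false-positive rate at 1 SD to 70%. The endpoint is worded as a plain comparison, which an unadjusted test answers. On this view a limitations sentence and a sensitivity analysis would be enough.

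Most of this stands as a limit on the claim. Nothing places the study in any particular row, and the extreme rows deserve little weight. The ROC calculation concerns areas; no cut-off was computed. Adjusting for age also removes confounding by age only.

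It does not remove the point. The choice of covariates should be fixed before results are seen, and nothing visible rules imbalance out. If age is balanced or matched, adjustment costs one degree of freedom. If it is not, adjusted linear power exceeds masked power in all 12 rows. The planned tests are kept, so the descriptive comparison is not lost.

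**Conclusion.** The concern holds as a conditional one. The design is observational, 15 elements are compared, only unadjusted tests are planned, and no matching is stated in the visible text. The size of any distortion cannot be derived from the documents. Over the assumed range, the per-element false-positive rate is 5.2% to 51% against a nominal 5%. Power at d = 0.60 falls from 0.84 to between 0.81 and 0.17 when the covariate acts against the group effect. The null ROC area is 0.507 to 0.611 instead of 0.500. These figures assume normally distributed data and a single covariate with a linear effect. The plan is not invalid for describing the two samples; what is limited is attributing a difference or a cut-off to POI. This is worth fixing, with medium confidence, because the gap is documented, its effect is unknown and the remedy is inexpensive.

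**What to change.** In section 2 (Baseline Characteristics):

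- Make the main analysis of each element a linear regression of concentration on group and age at enrolment, and report the adjusted difference with its 95% CI.
- Where Mann-Whitney would have been used, regress the ranks of the concentrations on the same two terms and report the adjusted rank difference and p-value. A rank difference is not in concentration units, so show group medians beside it.
- Keep the t-test and Mann-Whitney results as unadjusted, supportive results.
- Tabulate age and any other recorded covariates by group, and state any matching or age restriction used to select controls.
- Keep the ROC analysis, but label its cut-offs as unadjusted.

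In section 5 (Limitations and strengths), which currently gives only strengths, describe all results, including the cut-offs, as associations that may reflect group differences other than POI.

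**Cost.** SAP wording and 15 regressions, with no new participants or samples. This assumes age is recorded, which the visible text does not confirm. Adjustment uses one degree of freedom and loses precision when age differs strongly between groups: at 1 SD imbalance with r = 0.1 to 0.3, linear power is 0.76 to 0.80 by formula (0.761 to 0.795), just under the plan's 0.80 target. Unmeasured or poorly measured confounding remains.

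### ROC cut-offs are picked and judged in the same 50 + 50 women with no validation or optimism correction; if Youden-optimised, sensitivity and specificity are overstated by about 5 points each on average at d = 0.60

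*Combined protocol and SAP*

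**What the plan says.** The single sentence on diagnostic accuracy is in section 2 (Baseline Characteristics): "The ROC analysis will be applied for the determination of cut-off point for variables". The cut-off is therefore an output of this study's data, not a value fixed beforehand. Recruitment Details in section 1 describes one sample: "50 subjects with idiopathic POI, and 50 healthy patients were selected for the control group".

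The document does not say how the point on the curve is chosen, which accuracy figures will be reported, or how they will be validated. It mentions no split, second cohort, resampling or correction. Section 5 (Limitations and strengths) gives strengths only and does not raise the matter. On software, section 2 says: "SPSS for Windows 22.0 and Medcalc programs will be used for statistical analysis".

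Sections 3 and 4 make the concentrations of 15 elements, compared between the groups, the primary outcome. ROC analysis is not listed there.

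**The concern.** A threshold chosen because it best separates a given set of women fits the chance features of that set as well as any real difference. Measuring its sensitivity and specificity in the same women counts those chance features as accuracy. The error has a direction: on average the cut-off looks better than it would in new women. It is largest for weak or null elements, and with 15 elements under study some may be of that kind. A reader who took such a cut-off as a usable threshold would expect too much of it.

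**Working it through.** **Inputs.** From the document: 50 per group (Recruitment Details); d = 0.60, α = 0.05, power 0.80 and a minimum of 45 per group (section 2). Assumed, because the document is silent: the cut-off maximises the Youden index J = sensitivity + specificity − 1; data are normal with equal variance, or can be made so by a monotone transformation; no ties; one element at a time.

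**1. The plan's own figure.** For a two-sided t-test the noncentrality is d√(n/2) on 2n − 2 degrees of freedom. With n = 45 it is 0.60 × √22.5 = 2.85 and power is 0.804; with n = 44 power is 0.795. The stated 45 is reproduced. With n = 50 power is 0.844.

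**2. Benchmark without selection.** With controls N(0, 1) and POI N(d, 1), the best population cut-off is d/2 = 0.30. Sensitivity and specificity are both Φ(0.30) = 61.8%, so J = 0.236. In simulation a cut-off fixed in advance showed no bias (apparent J 0.236, true J 0.236).

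**3. Cut-off chosen in the sample.** In each simulated study the cut-off ĉ maximises the observed J. Its true sensitivity is 1 − Φ(ĉ − d) and its true specificity is Φ(ĉ). Optimism is apparent minus true. For 50 per group, d = 0.60, direction fixed, 20,000 runs:

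| | Apparent | True at chosen cut-off | Optimism |
|---|---|---|---|
| Sensitivity | 67.4% | 62.6% | 4.8 points |
| Specificity | 63.8% | 58.9% | 4.9 points |
| J | 0.312 | 0.216 | 0.096 |

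The Monte Carlo standard error is about 0.04 points. With 45 per group the optimism is 5.1 to 5.2 points each.

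**4. Range over effect sizes, 50 per group.** Points each = (apparent J − true J)/2. The fixed-direction rows up to d = 1.0 use 20,000 runs; all other entries use 10,000.

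| d | Direction fixed: apparent J / true J (points each) | Direction chosen from the data: apparent J / true J (points each) |
|---|---|---|
| 0 | 0.115 / 0 (5.8) | 0.164 / 0 (8.2) |
| 0.30 | 0.210 / 0.102 (5.4) | 0.214 / 0.090 (6.2) |
| 0.60 | 0.312 / 0.216 (4.8) | 0.314 / 0.215 (4.9) |
| 1.0 | 0.447 / 0.362 (4.2) | 0.447 / 0.362 (4.2) |
| 2.0 | 0.729 / 0.666 (3.2) | 0.726 / 0.666 (3.0) |

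**5. How often, and whether an interval covers it.** With direction chosen from the data, apparent J exceeds true J in 98% of samples at d = 0.30, 90% at 0.60 and 86% at 1.0. Those shares are for J. Taken singly at d = 0.60, sensitivity is overstated in about 80% of samples and specificity in 78–79%. The usual exact 95% interval at the chosen cut-off covers the true value about 93% of the time at d = 0.60, but lies wholly above it in 6.7% of cases (nominal 2.5%). At d = 0.30 coverage is 89–90%.

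**6. Effect of a bootstrap correction.** Cut-off and direction were re-selected in each resample (800 datasets × 200 resamples):

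| d | Apparent J | Corrected J | True J |
|---|---|---|---|
| 0 | 0.162 | 0.052 | 0 |
| 0.30 | 0.212 | 0.119 | 0.089 |
| 0.60 | 0.313 | 0.243 | 0.216 |
| 1.0 | 0.447 | 0.388 | 0.361 |

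At d = 0.60 the mean excess in J falls from 0.313 − 0.216 = 0.097 to 0.243 − 0.216 = 0.027. The root-mean-square error of J falls from 0.125 to 0.097, and the share of samples overstating J from 90% to 61%.

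**The case against.** The plan names neither the Youden index nor any report of sensitivity and specificity, and states no diagnostic aim. Strictly, the text shows an unspecified cut-off rule, and the 5 points are an illustration. This stands, and it is why the figure is given conditionally. But a cut-off that comes out of ROC analysis is ordinarily chosen for accuracy and reported with it, and the plan has nothing to prevent the bias.

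The size is also modest. Apparent sensitivity varies between samples with a standard deviation of about 15–16 points because the chosen cut-off moves, and the gap between apparent and true sensitivity in one sample has a standard deviation of about 6 points. Against the best population cut-off, rather than true performance at the chosen one, the excess is (0.312 − 0.236)/2 = 3.8 points. These facts limit the importance of the point but do not remove it: random error averages out over elements and studies, and optimism does not.

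The d of 0.60 was set to power a group comparison, not as an expected ROC separation, and the plan itself allows for non-normal variables. Ties, values below a detection limit and unequal spread were not simulated. The upper end of the range, 8.2 points, applies only to a null element whose direction is also chosen from the data.

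Finally, a plain caveat would deal with part of the concern. It would not give readers a less biased figure, which the bootstrap does at little cost.

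**Conclusion.** The concern holds, as a minor point. Followed in the ordinary way, the plan would give cut-offs whose stated accuracy is too high: about 5 points each for sensitivity and specificity at d = 0.60 with 50 per group, and roughly 3 to 8 points over the settings examined. This is an average, not a certainty in any one sample. It depends on a Youden-type choice, on accuracy being reported from the same women, and on the distributional assumptions listed above. The primary comparisons of the 15 elements are not affected.

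**What to change.** Replace the ROC sentence in section 2 with wording such as:

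> ROC analysis is exploratory and is reported for all 15 elements, whatever their p-value. AUC with its 95% CI is the main result. The cut-off is the value with the highest Youden index. Its sensitivity and specificity are reported as observed and after bootstrap optimism correction (1,000 resamples within group, cut-off and direction re-selected in each). Cut-offs need external validation. If single elements are highlighted because of their results, the report states that this correction does not cover that selection, or element selection is repeated in each resample.

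**Cost.** A change of wording and a short bootstrap script, run outside SPSS and Medcalc if needed; no new data. The reported accuracy will look slightly less favourable, and a small residual optimism remains.

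**Limit.** The correction does not cover picking an element after seeing the results. For the smallest p-value among 15 independent null elements, apparent J of 0.242 falls only to 0.161, or to 0.074 if element selection is repeated in each resample; the truth is 0. Multiplicity across the 15 group comparisons is a separate matter that this change does not address.
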